10.3 Primary Study Hypotheses

This is primarily an exploratory descriptive study that is not designed to test a hypothesis. However, the objectives of the study are based on the assumption that the "active" Wisebags will successfully and accurately record opening events, and will be acceptable for use by

women in the study, and that women will not be able to distinguish between an active and dummy Wisebag.

10.4 Number of Participants

The approximate sample size per site is estimated in Table 3.

Table 3: Approximate Number of Participants per Group

Device Group	Number of Participants
Dummy	10
Online	20
Offline	20
TOTAL	50

10.5 Data, Study Monitoring and Analysis

10.5.1 Study Monitoring Committee (SMC)

This is a brief pilot study, and no SMC review will be performed for this study.

10.5.2 Data Analysis

Performance endpoint

Performance will be assessed by comparing the number of failures (e.g., difficulties downloading stored data or receiving wireless data, battery- or signal-failures) experienced in each of the active-device groups. Questionnaire data reporting participants' user-related problems with the bag, device and/or battery will be tabulated overall and by randomization assignment. As indicated by the distribution of data, count data may be recoded and analyzed as categorical data. Count data will be compared using Poisson regression while categorical data will be compared using Chi-square tests. In cases of skewed data, alternative regression models may be implemented as appropriate.

Ability to Identify Randomization Arm

To assess blinding, the proportion of participants who are able to accurately identify whether they were randomized to the "dummy" or active-device groups will be reported. The proportion of participants who are able to indicate whether a demonstration bag is "dummy" or active (note that offline and online devices are identical, aside from the SIM card inside the online device), upon visual inspection, will also be reported. A summary statistic, such as the Cohen's kappa coefficient, will be used to summarize a) the level of agreement between the participant's response and the true group assignment and b) the level of agreement between the participant's response and the true bag type.

Concordance endpoint

Concordance between signal data and diary data will be summarized for participants assigned to the active device groups, and analysis will include the following: the proportion of participants whose number of events per signal data equals, exceeds, or is lower than the number of events per diary data. No formal testing will be performed on this endpoint.

Feasibility and acceptability endpoint

Feasibility and acceptability data collected at study exit by questionnaires will be summarized overall and by randomization group. No formal testing will be performed on this endpoint. Open-ended interview data will be tabulated, thematically coded and summarized by randomization group.

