2.4 Wisepill/Wisebag Technology

Wisebag™ (Wisepill Technologies Adherence Management Solutions, South Africa) is a portable, lunch-bag size container, which can contain approximately 30 individually wrapped gel applicators or more, closes with a zipper, and has a self-contained battery-operated electronic device that includes a chip which provides an electronic signal each time an opening event occurs, and counts and records any opening events, as well as a daily control signal ('heart beat') to signify proper battery functioning. Wisebag event monitoring system can be set-up such that all data are stored in the device until the information is downloaded at the clinic at follow-up visits (offline modality) or, each time an event occurs, a signal is sent to the central management system in real-time through a wireless system (online modality). Through this latter modality, it is possible to monitor adherence on an ongoing, 'real time' basis. The real time data capture and monitoring, although more expensive, allows up to the minute insight on patterns of use and non-use as well as the ability, where appropriate, to follow up with participants when non-adherent.

In recent HIV treatment studies, as described above, the Wisepill, a similar device using wireless technology to monitor tablet use, has allowed assessment of tablet-taking opening events in real time, and in combination with cell-phone reminders.^[15] In another recent study, Wisebag was piloted among 10 participants in the CAPRISA 004 trial, and this was the first application of such a technology to the microbicide context^[11]. Another pilot study currently being conducted in Uganda among 50 caretaker/infant pairs is using Wisebag for pediatric liquid HIV treatment in Uganda ([name], personal communication).

Like Wisepill and MEMS caps, the Wisebag electronic device monitors each opening event of the bag, and provides a date and time stamp of when these occurred. This non-invasive indirect objective approach to monitor adherence, has thus been adapted to monitor gel applicator use.

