Potential Use of Wisebag in VOICE: For women in the VOICE vaginal groups, use of the Wisebag would provide an objective measure of adherence that does not rely on participant self-report. A benefit of an electronic event-based monitoring system (as opposed to a low-tech, cross-sectional or serial cross-sectional approach such as unannounced product counts through home visits), is that it generates precise and detailed information on date and time of each event, allowing the research team to examine patterns of product use, product "holidays" etc. in addition to overall product adherence level. As described above, the technology was originally designed to serve two functions: a wireless opening-event monitoring system and an adherence intervention tool. The latter function, used in the 2 initial pilot studies from CAPRISA and in Uganda^[11, 15], uses a wireless cell phone technology to send a signal to a server when the bags are opened and send a real-time reminder to participants if events are not recorded within an expected timeframe. Additionally, the online functionality provides daily data on women, even if they forget to bring back their Wisebag at the next study visit. Given the wireless reporting capability of Wisebag, site staff will not be affected. Nevertheless, a simpler, cheaper version of the device is currently being developed for "offline" event monitoring (all opening signal events would be stored on the device's electronic chip and downloaded on a local server at study visits), providing only the assessment component (similar to a MEMS cap) which is the

functionality needed in VOICE. Furthermore, because of the relatively high cost of the current “active device” Wisebag (approximately \$200/bag), the Wisepill company can produce a “dummy” Wisebag which is identical looking, but has no recording system inside the device, in order to provide similar looking bags to all vaginal group women at a VOICE site, while collecting data only on a smaller subset.

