4.4 Time to Complete Accrual

The accrual period is targeted over approximately 8 weeks.

4.5 Study Groups:

The three study groups are as follows:

- "Dummy" or placebo Wisebag group: this group will receive a Wisebag which looks and feels identical to an active-device Wisebag, but has no battery or electronic recording system inside the device.
- "Online device" Wisebag: Active-device Wisebag with wireless component and SIM card for sending in real-time all opening events to a central server, in addition to a battery.
- "Offline device" Wisebag: Active-device Wisebag without the wireless component and the SIM card, and with battery and electronic recording system to store all opening events, which are then downloaded to a server at the clinic site.

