7.1 Screening and Enrollment

The Screening and Enrollment Visit for the Wisebag pilot should take place within approximately 4 weeks of the last VOICE Screening Visit; however participants may be enrolled up to 90 days after the date of the last VOICE Screening Visit. Screening for all data collection activities will include oral or written confirmation that participants meet the inclusion and exclusion criteria. Study staff will create checklists to ensure this is consistently documented.

Table 1: Screening and Enrollment

Screening and Enrollment	
Component	Procedures
Administrative and Regulatory	
 • Obtain informed consent • Confirm eligibility • Obtain locator information • Randomization • Schedule next (exit) visit • Provide counseling regarding protocol adherence • Provide reimbursement for study visit
Behavioral	
 • Conduct demographic and brief behavioral assessment • Dispense (2) weekly diary cards as well as the Wisebag along with instructions on use. • Practice opening/closing the bag and placing a study sticker on their diary card

7.2 Exit Visit: End of Week 2

Visit window at target exit visit date: The target visit exit date will be 2 weeks (14 days) from the enrolment date, with an allowable visit window of plus or minus 3 days. Participants who present late for their exit visit (Day 18 or later) will complete study procedures, as long as the study is still in the accrual phase. Otherwise, the participant will be classified as lost to follow up if they missed the exit visit window and there were 3 unsuccessful contact attempts.

Table 2: Exit Visit: End of Week 2

Week 3	
Component	Procedures
Administrative and Regulatory	
 • Collect Wisebag from participant. • Download data from the 2 week period from all “active” Wisebags • Provide reimbursement for study visit • Debrief on the full purpose of the research
Behavioral	
 • Conduct behavioral and acceptability assessment • Collect and review diary card • Semi-structured brief qualitative interview • Perceived Wisebag product

7.3 Interim Visits:

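### The online versus offline performance comparison counts failures without regard to opportunities or data lost, and so tends to favour offline

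*Protocol*

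**What the plan says.** The first primary objective (Section 3.1) is to compare the technical performance of the two active devices. Section 10.5.2 fixes the measure: "Performance will be assessed by comparing the number of failures (e.g., difficulties downloading stored data or receiving wireless data, battery- or signal-failures) experienced" in each active-device group. It goes on: "Count data will be compared using Poisson regression while categorical data will be compared using Chi-square tests". It also allows a change of scale: "As indicated by the distribution of data, count data may be recoded and analyzed as categorical data". It states no denominator or exposure offset, and it does not weight a failure by the data it loses. Performance is also the only endpoint for which tests between groups are specified. Concordance and acceptability are explicitly left untested, and blinding is summarised by proportions and an agreement coefficient.

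The two devices deliver data differently. For online, Section 2.4 says that "each time an event occurs, a signal is sent to the central management system in real-time through a wireless system (online modality"). For offline, "all data are stored in the device until the information is downloaded at the clinic at follow-up visits (offline modality"). Section 4.5 repeats that offline openings are stored on the device, "which are then downloaded to a server at the clinic site". Section 4.1 plans one follow-up visit, two weeks after enrolment. Section 2.4 gives as an advantage of online that "the online functionality provides daily data on women, even if they forget to bring back their Wisebag at the next study visit".

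**The concern.** A count of failures is a fair comparison only if both arms have the same number of chances to fail and a failure costs about the same in each. Neither holds for data transfer. Online has a chance to fail at each opening, and each miss costs one opening. Offline has one planned chance, and a miss can cost two weeks. Section 10.5.2 puts both into one count.

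Section 2.4 says the pilot will determine whether and how Wisebag is scaled up in a larger VOICE ancillary study. It already describes the offline device as simpler and cheaper. A measure that leans toward offline could appear to confirm that preference while offline captures less adherence data.

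**Working it through.** **The plan's own figures.** 50 × (1, 2, 2)/5 = 10 dummy, 20 online and 20 offline, as in Table 3. The protocol gives no failure rate, significance level or power for this comparison. Failure rates below are therefore assumptions, and a two-sided 5% level is assumed.

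**Transfer opportunities.** With one opening a day for 14 days (Sections 4.1 and 4.6):
- Online: 20 women × 14 = 280 transmissions.
- Offline: 20 women × 1 = 20 downloads.
- Ratio: 14 to 1.

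**Equal data loss.** Let 5% of transfers fail in each arm.
- Expected failures: 280 × 0.05 = 14 online, 20 × 0.05 = 1 offline.
- Device-days lost: 14 × 1 = 14 online, 1 × 14 = 14 offline.
- Poisson likelihood ratio without offset: 2 × [14 ln(14/7.5) + 1 ln(1/7.5)] = 13.4, p = 0.0002. The exact conditional test gives p = 0.001.
- Per opportunity: 14/280 = 5.0% and 1/20 = 5.0%, exact p = 1.0.

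**Simulation** (4,000 trials per setting, 20 versus 20). With transfer failures only and the same failure rate in both arms, the share of trials declaring offline better is:

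| Failure per transfer | 1% | 2% | 5% | 10% |
|---|---|---|---|---|
| Poisson, no offset | 45% | 76% | 98% | >99% |
| Chi-square, any failure versus none | 23% | 61% | 95% | >99% |

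A fair two-sided 5% test would favour offline in about 2.5% of trials. Recoding to any failure versus none does not cure the problem here.

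**Failures common to both devices.** Section 10.5.2 also counts battery and signal failures, and Section 2.4 describes the daily heart beat for Wisebag in general. A shared rate s per device-day adds 280 × s expected failures to each arm. At 5% transfer failure:

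| Shared daily failure | 0% | 2% | 5% | 10% | 20% |
|---|---|---|---|---|---|
| Expected failures, online v offline | 14 v 1 | 19.6 v 6.6 | 28 v 15 | 42 v 29 | 70 v 57 |
| Poisson favours offline | 98% | 76% | 53% | 34% | 18% |
| Chi-square favours offline | 95% | 59% | 33% | 14% | <1% |

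At 1% transfer failure with 10% shared failures the Poisson figure is 4%, so the bias has almost gone.

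**Unequal loss.** Let a fraction a of online transmissions and b of offline downloads fail. The share of data lost is a online and b offline. Expected counts are 280a and 20b, so they are equal when b = 14a. Between b = a and b = 14a, offline loses more data but has the lower expected count.
- a = 3%, b = 15%: 8.4 versus 3.0 failures, but 8.4 versus 3 × 14 = 42 device-days lost. Offline is declared better in 40% of trials and online in under 0.1%.
- a = 1%, b = 50% (beyond 14 × 1% = 14%): 2.8 versus about 10 failures. Online is declared better in 60%.
- a = 0%, b = 30%: 0 versus 6 failures. Online is declared better in 97%.

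**The case against.** A reader might infer that offline wins whatever data are lost. The last two scenarios show that this is wrong: a high enough download failure rate makes the count favour online.

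A reader might also infer that an offline bag can fail only once. That is true of data transfer alone. Battery and signal failures are in the list and can recur daily in either device. Table 2 also downloads all active bags at exit, online ones included. Online therefore has a download step that can fail too, and a missed transmission may not be lost for good. The protocol does not say whether the exit download recovers it.

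Section 10.5.2 leaves the unit of failure undefined. Repeated wireless trouble on one device could be logged once. The unit, or an offset, could be set in an analysis plan not seen here. An offset would correct the simple transfer case. A single offset does not suit a count that mixes transmissions, downloads and batteries, each with its own denominator and cost.

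Data loss is also examined elsewhere. Section 10.2 names signal accuracy by modality against the diaries as a separate outcome, Section 4.2 places diary and signal data within technical performance, and Section 10.5.2 reports how many women have fewer signals than diary entries. This stands in part. But that summary is untested, and a woman who does not return leaves neither diary nor offline record, so she drops out of it.

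The study is exploratory (Sections 2.6.1 and 10.3), and no section makes this test the rule for choosing a device. A reader might infer such a rule; the text supports only that the result will inform the choice. Nor does the list of failures exclude unreturned bags, since it gives examples only. Even if counted, though, an unreturned offline bag would add one failure for a whole lost record.

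Finally, Section 7.2 says that late attenders "will complete study procedures, as long as the study is still in the accrual phase". One might infer a large loss of offline data from this. It affects only women who are late and whose late visit falls after accrual closes, and the protocol gives no rate of lateness. It is a separate, minor point.

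**Conclusion.** The point holds as a tendency, not a certainty. The stated measure compares arms with about 14 to 1 transfer opportunities and ignores how much each failure costs. When data loss is equal or moderately worse offline, it leans toward offline. With transfer failures only and equal loss of 1% to 10%, the Poisson test declares offline better in 45% to more than 99% of trials. At 5% transfer failure the figure falls from 98% to 18% as shared daily failures rise from 0% to 20%. In expectation the direction reverses once the download failure rate exceeds 14 times the per-transmission rate.

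These sizes rest on assumed failure rates, one opening a day, independent failures, each missed signal counted once, and no recovery of missed transmissions at exit. The inequality of opportunities and of consequences rests on the protocol's own description. It is worth correcting because this is the first primary objective, but it does not invalidate the pilot.

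**What to change.** In Section 10.5.2, make the between-modality measure the proportion of expected device-days, per randomised woman, with usable data in the study database.

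- Report heart-beat capture and opening-event capture separately, the latter against diary-recorded openings. Accepting either signal for a day would hide lost openings behind a received heart beat.
- Count every day whose data were never retrieved as zero. For an offline bag that is unreturned, lost or cannot be downloaded, that means all its days, not only those after the loss.
- For online bags, report data received wirelessly separately from data recovered at the exit download.
- Give the online minus offline difference with a 95% confidence interval, and the number of women in each arm with all data lost.
- Keep failure types as a descriptive table, each with its own number of opportunities.

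The signals and diaries are already collected, so the cost is a wording change, one derived variable and a little more analysis. The late-exit rule in Section 7.2 can be considered separately.

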4 STUDY DESIGN

4.1 Identification of Study Design

MTN-003-P01 is a three-arm, randomized, placebo-controlled, double-blinded pilot study of Wisebag for monitoring daily product use. The study is double-blinded with respect to participants and investigators, (but not for pharmacy and information technology (IT) staff who will manage the download of the electronic data and the battery charging of Wisebag devices). Approximately 50 participants will be randomized to the 3 study arms in a 1:2:2 ratio. The 3 groups will be “dummy” Wisebag (n~10) “Online device” Wisebag (n~20), or “Offline device” Wisebag (n~20).

There will be two study visits: an enrollment visit and one follow-up/exit visit, two weeks after enrollment. During study participation, participants will be asked to open their assigned Wisebag at approximately the same specified time daily, to peel off one sticker from a set of study stickers inside the bag, and place the sticker on the appropriate day of the week on a study provided diary card. After two weeks of daily openings, participants will be asked to return to the study clinic for an exit visit with their Wisebag and diary card.

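### If failure counts are recoded into three or more levels, the Chi-square test named in 10.5.2 ignores their order and loses power at about 20 v 20; an ordered or rank test is a cheap improvement

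*Protocol*

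**What the plan says.** Protocol section 10.5.2 assesses performance by "comparing the number of failures (e.g., difficulties downloading stored data or receiving wireless data, battery- or signal-failures) experienced in each of the active-device groups". It then sets out three routes for the analysis.

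- Default: "Count data will be compared using Poisson regression while categorical data will be compared using Chi-square tests".
- Optional recode, depending on how the data turn out to be distributed: "count data may be recoded and analyzed as categorical data".
- Skewness: "In cases of skewed data, alternative regression models may be implemented as appropriate".

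The section gives no number of categories, no cut-points, and no ordered or exact test. On size, section 4.1 states: "Approximately 50 participants will be randomized to the 3 study arms in a 1:2:2 ratio". That makes about 20 online and about 20 offline participants, as in Table 3 of section 10.4.

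The comparison serves the first-listed primary objective in section 3.1. It is also the only endpoint with named between-group tests. Blinding is summarised by proportions and an agreement coefficient, and the concordance and acceptability paragraphs of 10.5.2 both rule out formal testing.

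**The concern.** Each active device gives a daily control signal (section 2.4) and each woman is followed for about 14 days (section 4.6). Some women may therefore have several failures while many have none, and a distribution of that kind invites recoding. Once counts become 0/1/2+ or 0/1/2/3+, the categories still run from fewer to more failures. An ordinary chi-square test gives the same p-value however the columns are shuffled, and it spends one degree of freedom per category beyond the first. It therefore looks for any difference in pattern instead of an excess of failures in one device.

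What is at stake is efficiency. A real excess in one modality becomes harder to show, in a study with about 40 informative participants whose results are meant to guide whether and how Wisebag is scaled up (section 2.4).

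**Working it through.** **Inputs from the protocol.** Total about 50 in ratio 1:2:2: 50 × 1/5 = 10, 50 × 2/5 = 20, 50 × 2/5 = 20. This agrees with Table 3. The protocol states no power, alpha, failure rate or effect, so there is no power figure to reproduce.

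**Assumed inputs.** Two-sided 5%; mean failures per woman from 0.1 to 4; Poisson or negative binomial counts (dispersion k = 1, or 0.5 where stated); recodes none/any, 0/1/2+ and 0/1/2/3+.

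**Formulas.** Let a_j and b_j be the numbers of women in category j in the two arms of 20, and c_j = a_j + b_j.

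- Pearson chi-square: each expected cell is c_j/2, so X² = Σ (a_j − b_j)²/c_j on (number of levels − 1) degrees of freedom. The category's position does not enter.
- Trend: with scores s_j = 0, 1, 2, … and s̄ = Σ s_j c_j/40, z = (Σ s_j a_j − 20 s̄)/√(V × 20 × 20/40), where V = Σ (s_j − s̄)² c_j/39. The position does enter, on one degree of freedom. With two levels the two tests coincide.

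**Sparseness.** An expected cell is below 5 when c_j < 10. Four columns share 40 women, so all expected cells reach 5 only if every column holds exactly 40/4 = 10. In simulation a cell fell below 5 in 98% to 100% of four-level tables. With three levels the share was 43% to 100%.

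**Power (%), 20 v 20, 3,000 runs per row (selected scenarios).**

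| Means | Counts | Chi-square, none/any | 3 levels: chi-square → trend | 4 levels: chi-square → trend | Wilcoxon, raw counts |
|---|---|---|---|---|---|
| 0.3 v 1.0 | Poisson | 66.2 | 65.9 → 77.8 | 54.4 → 78.3 | 75.6 |
| 0.5 v 1.2 | Poisson | 47.1 | 52.1 → 62.6 | 41.8 → 65.7 | 63.4 |
| 1 v 2 | Poisson | 40.6 | 51.7 → 61.0 | 50.9 → 68.8 | 68.7 |
| 1 v 3 | Poisson | 76.9 | 93.2 → 96.4 | 96.0 → 99.0 | 99.3 |
| 2 v 4 | Poisson | 20.7 | 52.5 → 65.4 | 69.1 → 84.1 | 93.6 |
| 0.3 v 1.0 | k = 1 | 41.6 | 39.0 → 50.5 | 28.0 → 52.9 | 48.7 |
| 1 v 2 | k = 1 | 18.2 | 20.5 → 25.6 | 20.3 → 30.9 | 30.4 |
| 2 v 3.2 | k = 1 | 10.8 | 11.2 → 13.2 | 11.2 → 16.3 | 18.6 |

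Over all 16 non-null scenarios of this run, the loss from ignoring order was 2 to 13 points with three levels (median about 8) and 3 to 25 with four (median about 17). At lower means (0.1 v 0.4 to 0.2 v 0.8; 4,000 runs) it was 13 to 19 with three levels and 16 to 29 with four. A further set of assumed rates gave 5 to 21 and 11 to 34. Taken together: about 2 to 20 points for three levels and about 3 to 35 for four.

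**Two levels.** The loss from order is 0. Dichotomising can still cost power against Wilcoxon on the raw counts: 7 to 73 points at means from 0.3 v 1.0 to 2 v 4. At the lower means it costs about 0 to 5 points (for example, 45 v 46 for Poisson 0.1 v 0.4 and 52 v 56 for k = 1, 0.2 v 0.8).

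**Permutation version.** With means 0.5 v 1.5, four-level chi-square against a permutation rank test on raw counts gave 37% v 52% at k = 1 and 24% v 35% at k = 0.5.

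**Null rejection.** Chi-square on three or four levels: 2.7% to 5.3%. Permutation rank test: 3.7% to 5.1%. Plain Poisson regression is not a fair benchmark, because it rejected 12% to 25% under the null at k = 1.

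**The case against.** The strongest reply has four parts.

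1. Recoding is optional, Poisson regression is the default, and the sentence on skewed data already offers a route that keeps counts as counts. This stands as a limit on how often the loss would occur. It does not change the test once counts have been recoded.
2. The number of levels is not in the protocol. If most women have no failure, none/any is the obvious recode, and there the loss from order is nil. This stands, and it is why no single figure can be given. A reader might infer a fixed loss of, say, 5 to 15 points. The documents do not support that: the loss runs from 0 to about 35 points with the cut-points and the assumed rates.
3. The wording is Chi-square tests in general, and a linear trend test is also a chi-square test. Reading it as the ordinary unordered test is the natural reading, but it is a reading. If the unseen SAP names the trend form, the point is met.
4. The study is declared exploratory, not designed to test a hypothesis (sections 2.6.1 and 10.3), and sets no power target. This lowers the weight. It is no reason to prefer the weaker test in a primary comparison for which tests are named.

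**Conclusion.** The point holds as an efficiency weakness that is cheap to remove. If failure counts are recoded to three or more levels and tested by ordinary chi-square, the online-versus-offline comparison loses about 2 to 20 points of power with three levels and about 3 to 35 with four, against an ordered test. With none/any the loss from order is 0. Dichotomising itself then costs little when failures are rare and can cost much when several failures per woman are common. All of these figures rest on assumed failure rates, dispersion, cut-points and a two-sided 5% level, and on the recode being used at all.

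Two stronger readings are tempting and not supported. A reader might infer that sparse tables inflate false positives; null rejection stayed at about 2% to 5%. A reader might also infer that the protocol commits the primary comparison to this test; it only permits it.

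**What to change.** In section 10.5.2:

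- Keep the count regression, including the alternative regression models for skewed data, as the source of the rate ratio and its confidence interval.
- Where a count model does not fit, compare the unrecoded per-woman failure counts between online and offline by a Wilcoxon rank-sum test with a permutation p-value. Use categories for display.
- If ordered categories are tested, use an exact trend (linear-by-linear) test, with cut-points fixed beforehand.
- Keep Chi-square for yes/no or unordered items.

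The cost is a small edit to one paragraph and no new data. The downside is that a rank or trend test gives no rate ratio, which is why the regression should stay, and it is less sensitive than chi-square to a difference that does not run in one direction.

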In this Wisebag Pilot Study, we will test several of its new functionalities that will determine whether and how to scale up its implementation as part of a larger VOICE ancillary study on objective measures of product use. The new features tested in this pilot study will include: a) use of the “offline” monitoring functionality, b) use of a “dummy” Wisebag in a blinded fashion and c) monitoring of **daily** product use among ~ 50 South African women at a site determined by the EC, in a population similar to that enrolled in VOICE, using study stickers stored in the Wisebag.

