3 OBJECTIVES

3.1 Primary Objectives

- To compare the on-site technical performance of the “offline” and “online” functionalities of Wisebag
- To assess the success of attempted blinding of the “dummy” vs. active (“online” or “offline”) Wisebag
- To measure the concordance between Wisebag opening-event data (both “online” and “offline”) and self-reported data.
- To explore the feasibility and acceptability of Wisebag use by participants

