4.6 Expected Duration of Participation

Once enrolled, each participant is expected to complete approximately 2 weeks (14 days \pm 3 days) on the study.

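### For online versus offline performance, 10.5.2 names tests on about 20 v 20 women and no confidence interval, so a non-significant result would be weak evidence of similar performance.

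*Protocol*

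**What the plan says.** Protocol 3.1 lists first among the primary objectives: "To compare the on-site technical performance of the “offline” and “online” functionalities of Wisebag". Section 4.1 sets the size: "Approximately 50 participants will be randomized to the 3 study arms in a 1:2:2 ratio", which gives about 10 dummy, 20 online and 20 offline. On follow-up, 4.6 says that "each participant is expected to complete approximately 2 weeks".

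Section 10.5.2 assesses performance by comparing the number of failures in the two active-device groups, and it tabulates user-reported problems overall and by arm. It then names the methods: "Count data will be compared using Poisson regression while categorical data will be compared using Chi-square tests". Other regression models are allowed if the data are skewed. For concordance and for feasibility and acceptability, the same section expressly rules out formal testing. It makes no such exclusion for performance.

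Sections 2.6.1 and 10.3 describe the study alike: "This is primarily an exploratory descriptive study that is not designed to test a hypothesis". On the use of the results, 2.4 says that "we will test several of its new functionalities that will determine whether and how to scale up its implementation", with the offline device described there as the simpler and cheaper version.

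The protocol gives no significance level, expected failure rate, relevant difference, margin or precision for this comparison.

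**The concern.** The aim is descriptive, but the only named way of comparing the two devices is by regression or test, and the protocol sets no precision for the answer. Those planning the larger VOICE ancillary study need to know how often each device could fail and how much worse one could be than the other. A Chi-square p-value gives neither. Section 2.6.2 says that the offline mode had not been tested before. A p-value above 0.05 between it and the online device could easily be summarised as the two performing alike. If so, a device with a materially higher failure rate could go forward without the uncertainty being visible.

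**Working it through.** **Inputs from the protocol.** About 50 women in a 1:2:2 ratio: 50 × 1/5 = 10 and 50 × 2/5 = 20, so 10/20/20, which matches 4.1 and Table 3 in 10.4. There is no power or precision statement to reproduce.

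**Assumptions.** Two-sided 5% level, no dropout, and failure rates as listed below. For the proportions, each woman counts once: her device failed or it did not.

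**Chi-square power at 20 v 20.** With a and b failures, the uncorrected statistic is X² = (a/20 − b/20)² / [p̄(1 − p̄)(2/20)], where p̄ = (a + b)/40. Power is the sum of Bin(a; 20, p₁) × Bin(b; 20, p₂) over all 21 × 21 outcomes with X² ≥ 3.84. The miss rate is 1 − power.

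| Failing, one arm v other | Chi-square power | Missed | Fisher power |
|---|---|---|---|
| 5% v 20% | 0.292 | 71% | 0.168 |
| 10% v 30% | 0.357 | 64% | 0.242 |
| 5% v 25% | 0.444 | 56% | 0.299 |
| 0% v 20% | 0.589 | 41% | 0.370 |
| 10% v 50% | 0.838 | 16% | 0.742 |

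By the normal approximation, 80% power for 10% v 30% needs 62 women per arm.

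**What an observed result would show.**
- 6/20 v 2/20: p̄ = 0.20, X² = 0.20² / (0.20 × 0.80 × 0.10) = 2.5, p = 0.11. The Newcombe 95% interval for the difference is -5 to +43 points.
- 7/20 v 2/20: X² = 0.25² / (0.225 × 0.775 × 0.10) = 3.58, p = 0.058. With 2/20 in one arm, the other must reach 8/20 (X² = 4.8, p = 0.028) to be significant.
- 2/20 v 2/20: p = 1.00. The Wilson limits for 2/20 are 0.028 and 0.301, so the Newcombe half-width is √[(0.100 − 0.028)² + (0.301 − 0.100)²] = 0.214, an interval of -21 to +21 points.
- 0/20 in one arm: exact (Clopper-Pearson) upper limit = 1 − 0.025^(1/20) = 0.168, or 16.8%.

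**Counts.** Arm totals are taken as Poisson with mean 20m, where m is the mean number of failures per woman. The likelihood-ratio test rejects when 2[a ln a + b ln b − (a + b) ln((a + b)/2)] ≥ 3.84. Power is 36% for means of 0.1 v 0.3, 27% for 0.25 v 0.5, 46% for 0.5 v 1, 75% for 1 v 2 and 96% for 2 v 4. Overdispersion would lower these figures.

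**The case against.** Four stronger readings are tempting, and the protocol does not support them.

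- **That the objective is answered only by significance tests.** Section 10.5.2 also counts failures and tabulates user-reported problems by arm. Poisson regression yields a rate ratio from which an interval follows directly.
- **That the protocol will treat a non-significant result as equal performance.** It says so nowhere. It sets no significance level, success criterion or go/no-go rule, and 2.4 ties scale-up to no p-value. The misreading is a foreseeable risk, not a planned inference.
- **That the test usually misses a relevant excess.** No relevant excess is defined. Large excesses and frequent failures are mostly detected, and even 0% v 20% is found in 59% of trials.
- **That 10.3 and 10.5.2 contradict each other.** The study is only primarily descriptive, so exploratory tests can stand beside that statement. It is a tension.

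It can also be said that interval methods and table layouts commonly belong in a statistical analysis plan, which is not at hand and may supply them. That argues against treating this as an omission. It does not remove the point, because the protocol itself fixes the method of comparison, and that method serves the descriptive aim less well than estimation would. Lastly, 10.4 labels its table as per site. If several sites each enrolled 50 women, power would be higher, but 2.5 and 4.1 give about 50 in all.

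**Conclusion.** The point holds as a limited one on the choice of analysis. For a primary objective, the protocol names tests where estimates with intervals would suit its stated aim better. At about 20 v 20, a null result is weak evidence of similarity: for contrasts such as 5% v 20% or 10% v 30%, the Chi-square test misses the difference in roughly two thirds of trials or more, and identical observed failures cannot exclude an excess of about 21 points in either direction. The miss rates rest on assumed failure rates, a two-sided 5% level and one yes/no outcome per woman. The intervals depend only on the observed counts and 20 women per arm. The tests named are not invalid, and the protocol plans no wrong conclusion. This is an inexpensive improvement that limits what can be concluded from a null result.

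**What to change.** In 10.5.2, make estimation the main performance result:

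- for each active arm, the proportion of women with a device failure, with an exact 95% interval;
- the offline-minus-online difference in that proportion, with a 95% interval (for example Newcombe);
- for failure counts, the rate ratio with its 95% interval from the regression already named.

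Keep any Chi-square or Poisson test as supportive, and add a sentence such as: *A non-significant difference between the modalities will not be taken as evidence that they perform equally.*

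Do not add a rule that bases scale-up on the upper confidence limits. The protocol defines no acceptable failure rate, so such a rule could not be applied.

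The cost is a few lines of text and some extra table columns, with no more participants or data. The downside is that wide intervals will make the stated conclusion about the two devices less favourable.
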